#### 8.1.4 Storage and Stability

Please refer to pharmacy manual for detailed instructions

Clinical supplies must be stored in a secure, limited-access location under the storage conditions specified on the label.

Store Pembrolizumab vials under refrigeration at 2 to 8 degrees Celsius (°C) or 36 to 46 degrees Fahrenheit (°F). Do not freeze; do not shake.

Prior to reconstitution, the vials of lyophilized powder can be out of refrigeration (temperatures at or below 25°C (77°F)) for up to 24 hours.

Storage following reconstitution and dilution: Store at room temperature for a cumulative time up to 4 hours (this includes room temperature storage of the diluted infusion solution and the duration of infusion). IV bags and/or reconstituted vials can be also stored refrigerated at 2—8 degrees °C (36—46 degrees °F) for up to 20 hours. If refrigerated, allow the vials and/or IV bags to come to room temperature prior to use. Do not freeze.

Receipt and dispensing of trial medication must be recorded by an authorized person at the trial site.

Clinical supplies may not be used for any purpose other than that stated in the protocol.

**8.1.5 Protocol dose specifics**

200mg IV once every 3 weeks until disease progression or unacceptable toxicity. Pembrolizumab 200 mg will be administered as a 30 minute IV infusion every 21 days. A window of -5 minutes and +10 minutes is permitted (i.e., infusion time is 30 minutes: -5 min/+10 min).

**8.1.6 Preparation**

Please refer to pharmacy manual for detailed instructions.

Pembrolizumab is provided as a white to off-white lyophilized powder (50 mg/vial) or as a liquid solution (100 mg/vial) in Type I glass vials intended for single use only. Pembrolizumab is formulated with L-histidine as buffering agent, polysorbate 80 as surfactant, sucrose as stabilizer/tonicity modifier, and hydrochloric acid (HCl) and/or sodium hydroxide (NaOH) for pH adjustment (if necessary).

Pembrolizumab Powder for Solution for Infusion is reconstituted with 2.3 mL sterile water for injection (SWFI) to yield a 2.4 mL solution containing 25 mg/mL of pembrolizumab prior to further dilution. Pembrolizumab vial contains an excess fill of 10 mg (equivalent to 0.4 mL of reconstituted solution) to ensure the recovery of label claim of 50 mg/2 mL pembrolizumab per vial.

The product after **reconstitution with sterile water for injection** and the liquid drug product is a clear to opalescent solution, which may contain extraneous and proteinaceous particulates. The reconstituted drug product solution and liquid drug product are to be further diluted with normal saline in polyvinyl chloride (PVC) or non-PVC IV bags to achieve final concentration between 1 mg/mL and 10 mg/mL.

Reconstituted vials and infusion solutions should be immediately administered after preparation. If not used immediately, reconstituted vials and/or IV bags may be stored at 2-8 °C for up to a cumulative time of 20 hours. If refrigerated, the vials and/or IV bags should be allowed to equilibrate to room temperature prior to subsequent use. Pembrolizumab solutions may be stored at room temperature for a cumulative time of up to 4 hours. This includes room temperature storage of reconstituted drug product solution and liquid drug product in vials, storage of infusion solution in the IV bag and the duration of infusion.

**8.1.7 Route of administration for this study**

Intravenous (IV)

**8.1.8 Incompatibilities**

None known

Refer to pharmacy manual for list of infusion set materials compatible with pembrolizumab.

**8.1.9 Availability & Supply**

Merck will supply pembrolizumab (investigational / clinical supply) directly to the NU Investigational Pharmacy at no charge to subjects participating in this clinical trial. The contact for drug ordering will be [name]

([[name]\\[contact]](mailto:[contact])) or [name] ([[contact]](mailto:[contact])). The Merck Drug Request Form, provided by Merck, should be completed and emailed to these contacts.

The treating investigator shall take responsibility for and shall take all steps to maintain appropriate records and ensure appropriate supply, storage, handling, distribution, and usage of investigational product in accordance with the protocol and any applicable laws and regulations.

#### 8.1.10 Side effects

Pembrolizumab is generally well tolerated and demonstrates a favorable safety profile in comparison to chemotherapy. Pembrolizumab is an immunomodulatory agent, and based on this mechanism of action, immune mediated adverse events are of primary concern. Important identified risks for pembrolizumab are of an immune mediate nature, including: pneumonitis, colitis, thyroid disorders (hypothyroidism/hyperthyroidism), hepatitis, hypophysitis, Type I diabetes mellitus, uveitis, and nephritis. After a recent review of data, events newly characterized as identified risks also include pancreatitis, myositis, and severe skin reaction; these are included in the reference safety information in the current IB. The majority of immune-mediated adverse events were mild to moderate in severity, were manageable with appropriate care, and rarely required discontinuation of therapy.

In addition to the previously noted identified risks, infusion-related reactions are a risk but are not considered immune mediated; these are also further described in the current IB.

*Most common (seen in >10% of patients):*

- *Fatigue*
- *Headache*
- *Chills*
- *Difficulty sleeping*
- *Dizziness*
- *Leg swelling*
- *Itching and/or rash*
- *Elevated blood sugar level*
- *High triglycerides (type of cholesterol)*
- *Lower levels of calcium or sodium in the blood*
- *Nausea and/or vomiting*
- *Decreased appetite*
- *Diarrhea or constipation*
- *Pain in the abdomen*
- *Cough*
- *Shortness of breath*
- *Fever*

*Less common (seen in 1 to 10% of patients):*

- *Skin infection*
- *Abnormal thyroid function (decreased or increased)*
- *Colitis (inflammation or infection of the colon [large intestine])*
- *Sepsis (infection in the bloodstream)*
- *Kidney failure*

- *Pneumonitis (inflammation of the lung) or pneumonia (infection in the lung)*

*Rare but serious or life-threatening (seen in <1% of patients)*

- *Immune system attacking adrenal gland (adrenocortical insufficiency), joints (arthritis), liver (hepatitis), kidneys (nephritis), skin (dermatitis) muscles (myositis), eyes (optic neuritis or uveitis), pancreas (pancreatitis), brain (partial epilepsy), heart (immune-mediated myocarditis) or other organs causing possibly irreversible damage to these organs.*
- *Stevens-Johnson Syndrome and Toxic Epidermal Necrolysis have also been identified as rare but serious life-threatening side-effects.*
- *Sarcoidosis is a clinically significant, immune-mediated adverse reaction that was reported in less than 1% of patients*
- *Encephalitis is a clinically significant, immune-mediated adverse reaction that was reported in less than 1% of patients*

Please refer to the current version of the Investigator's Brochure for a complete list of adverse events.

#### **8.1.11 Nursing implications**

Pembrolizumab will be administered at 200mg IV on Day 1 of each cycle (1 cycle=21 days).Capecitabine will be administered at 1000 mg/m^2 BID D1-14 q21d. Patients will be instructed to take the morning dose of capecitabine before coming to clinic for pembrolizumab infusion (Refer to section 4.0 for details)

Pembrolizumab will be administered as an IV infusion ((section 8.1.6) over approximately 30 minutes Every effort should be made to target infusion timing to be as close to 30 minutes as possible. However, a window of -5 minutes and +10 minutes is permitted (i.e., infusion time is 30 minutes: -5 min/+10 min). Sterile, non-pyrogenic, low-protein binding 0.2 to 5 µm in-line filter made of polyethersulfone (PES) must be used during administration.

When an IV bag is used for the infusion, the IV line will be flushed with a volume of normal saline equal to the priming volume of the infusion set used after the contents of the IV bag are fully administered

Since the compatibility of pembrolizumab with other IV medications and solutions, other than normal saline (0.9% [w/v] sodium chloride for injection) and D5W , is not known, the Pembrolizumab solution should not be infused through an IV line in which other solutions or medications are being administered. The date, start time, interruption, and completion time of Pembrolizumab administration must be recorded in the source documents. Any unused solution for injection should not be used for another infusion of the same or different subject.

#### **8.1.12 Return and Retention of Study Drug**

The investigator is responsible for keeping accurate records of the clinical supplies received from Merck or designee, the amount dispensed to and returned by the subjects and the amount remaining at the conclusion of the trial.

Upon completion or termination of the study, all unused pembrolizumab vial(s) shall be returned to the designated facility for destruction.

Please refer to pharmacy manual for the address of the designated facility.

All used and/or partially used investigational product will be destroyed at the site per institutional policy. It is the Investigator's responsibility to arrange for disposal of all empty containers, provided that procedures for proper disposal have been established according to applicable federal, state, local and institutional guidelines and procedures, and provided that appropriate records of disposal are kept.

## **8.2 Capecitabine**

### **8.2.1 Other Names**

Xeloda

### **8.2.2 Classification – Type of Agent**

Antineoplastic Agent, Antimetabolite (Pyrimidine Analog)

### **8.2.3 Mode of action**

Capecitabine is a prodrug of fluorouracil. It undergoes hydrolysis in the liver and tissues to form fluorouracil which is the active moiety. Fluorouracil is a fluorinated pyrimidine antimetabolite that inhibits thymidylate synthetase, blocking the methylation of deoxyuridylic acid to thymidylic acid, interfering with DNA, and to a lesser degree, RNA synthesis. Fluorouracil appears to be phase specific for the G1 and S phases of the cell cycle.

### **8.2.4 Storage and stability**

Capecitabine is commercially available as 150 mg or 500 mg tablets. Physician may prescribe either 150mg or 500mg tablets based on calculation of patient's BMI

Capecitabine tablets should be stored at room temperature (15° to 30°C) in the container in which they are provided.

Patient will keep medication in a cool, dry place out of reach of children and other individuals.

### **8.2.5 Protocol dose specifics**

Patient to take capecitabine 1000mg/ /m^2 BID D1-14 of a 21 day cycle.

Capecitabine will be taken orally. It is self-administered by patient. Patients will be instructed to take the morning dose of capecitabine before coming to clinic for pembrolizumab infusion.

Capecitabine is to be taken preferably 12 hours apart (with minimum 8 hours between doses).

It is to be ingested with food or within 30 minutes of eating with 8 oz glass of water (not fruit juices). Tablets are to be swallow whole and not crushed or cut.

If dose is missed and next dose would normally be in less than 8 hours, then dose should be skipped entirely and marked accordingly on the medication diary (available as stand-alone document).

### **8.2.6 Preparation**

Film coated tablets

### **8.2.7 Route of administration for this study**

Oral. Self-administered by patient.

### **8.2.8 Incompatibilities**

Potential drug interactions: Capecitabine is a strong inhibitor of CYP2C9 and concomitant administration of CYP2C9 substrates should be avoided (ex: bosentan, cannabis, carvedilol, diclofenac, dronabinol, fosphenytoin, lacosamide, metronidazole, ospemifene, parecoxib, phenytoin, ramelteon, warfarin).

Warfarin: [US Boxed Warning]: Capecitabine may increase the anticoagulant

effects of warfarin; bleeding events, including death, have occurred with concomitant use. Clinically significant increases in prothrombin time (PT) and INR have occurred within several days to months after capecitabine initiation (in patients previously stabilized on anticoagulants), and may continue up to 1 month after capecitabine discontinuation. May occur in patients with or without liver metastases. Monitor PT and INR frequently and adjust anticoagulation dosing accordingly. An increased risk of coagulopathy is correlated with a cancer diagnosis and age >60 years.

Leucovorin Calcium-Levoleucovorin: May enhance the adverse/toxic effect of Capecitabine. *Risk C: Therapy to be monitored.*

Capecitabine may enhance the immunosuppressive effect of Immunosuppressants (ex: Leflunomide, Tacrolimus, etc.) concomitant administration is prohibited.

Vaccines (Live): Immunosuppressants may enhance the adverse/toxic effect of Vaccines (Live). Immunosuppressants may diminish the therapeutic effect of Vaccines (Live). Management: Avoid use of live organism vaccines with immunosuppressants; live-attenuated vaccines should not be given for at least 3 months after immunosuppressants.

Cimetidine: Since cimetidine can decrease the clearance of 5-FU, co-administration should be avoided. Ranitidine or a drug from another anti-ulcer class can be substituted for cimetidine if necessary.

For a complete and detailed list, please refer to FDA website:  
<http://www.fda.gov/Drugs/DevelopmentApprovalProcess/DevelopmentResources/DrugInteractionsLabeling/ucm093664.htm>

### 8.2.9 Availability & Supply

Capecitabine is standard of care treatment for metastatic breast cancer and will be provided through patient's insurance. Patients will be given a 14 days supply of tablets at the start of study treatment (patients will collect the tablets from their respective pharmacies). Additional capecitabine tablets will be dispensed every 3 weeks. The consent form will also ask that patients agree to keep the capecitabine pills out of reach from children and other individuals in their home.

### 8.2.10 Side effects

Frequency listed derived from monotherapy trials. Incidence reported for all indications and usage, unless otherwise noted. Frequency not always defined.

***Most common (seen in >10% of patients):***

- Fatigue
- Diarrhea
- Nausea and/or vomiting
- Decreased appetite
- Numbness or tingling
- Weakness
- Rash on the palms or soles
- Leg swelling
- Lowering of the white blood cell count or platelet count
- Anemia
- Higher levels of bilirubin in the blood
- Eye irritation
- Fever

- *Less common (seen in 1 to 10% of patients):*
- Blood clot in the veins
- Chest pain
- Irregular heart rhythms
- Fluid around the heart
- Heart stopping
- Heart attack
- Headache
- Dizziness
- Depressed mood or mood changes
- Difficulty swallowing
- Feeling sleepy
- Skin rash
- Hair loss
- Itching
- Increased thirst
- Hot flashes
- Lowering of the potassium or magnesium levels in the blood
- Weight gain
- Pain in your belly/indigestion
- Bleeding in the GI tract
- Feeling bloated
- Abnormal liver tests in the blood
- Hypersensitivity (allergic) reaction
- Back pain
- Muscle and/or joint aches
- Cough
- Shortness of breath
- Flu-like symptoms
- Coughing up blood
- Hoarse voice
- Nose bleeds

*Rare but serious or life-threatening (seen in <1% of patients)*

- Kidney failure (usually reversible)
- Fluid buildup in the abdomen
- Bronchitis and/or pneumonia
- Stroke
- Confusion
- Passing out
- Blood clots
- Sepsis (infection in the bloodstream)
- Stevens-Johnson syndrome (allergic reaction)

## **9.0 CORRELATIVES/SPECIAL STUDIES**

### **9.1 PD-L1 testing**

A baseline tissue biopsy of a metastatic will be obtained for PD-L1 immunohistochemical (ICH) assessment from all patients no more than 2 months prior to registration. An archived specimen may be used (metastatic tissue only) if collected no more than 2 months prior to registration. Otherwise fresh biopsy of metastatic lesion is mandatory at baseline and should be performed no more than 2 months prior to registration. The requirement for biopsy (fresh) may be

IRB #: STU00203215 Approved by NU IRB for use on or after 9/16/2019 through 9/15/2020.  
omitted per treating physician's discretion, if the biopsy  
would cause undue morbidity to the patient and if enough tissue from a prior  
metastatic lesion (archival biopsy) is not available.

QualTek developed and validated a PD-L1 IHC assay using  
Merck's proprietary 22C3 antibody, and will be used for this study.

The study site's pathology core will be used to store, process, and ship samples  
to QualTek.

For patient samples, positively charged ProbeOn Plus slides (**Fisher ProbeOn  
Plus Catalog Number 22-230-900**) must be used for tissue sections. Slide  
measurements should strictly be 75mm x 25mm x 1mm. Other standard-sized  
positively-charged slides (75mm x 25 mm x 1mm) are acceptable as a last resort,  
however QualTek must be notified as there is a risk that outside slides cannot be  
stained. The slides must be sized as described above or the sample **cannot be  
tested and will be returned.**

Tumor tissue for biomarker analysis must be provided as **five (5) freshly cut,  
serially sectioned, unstained slides** cut at 4 microns per patient for PD-L1  
testing.

Storage and Shipping: Samples may be held as blocks indefinitely at the site and  
then cut in batches. Slides must be shipped to QualTek immediately after  
sectioning to comply with the protocol's testing requirements. Patient slides must  
be shipped within seven (7) days of sectioning. Slides must be shipped cold (2-  
8°C) and in the dark.

See *QualTek MISP Sample Handling Manual* (available as stand-alone  
document) for detailed information regarding the processing, labelling and  
shipping of tissue samples prior to shipment.

Samples are to be shipped to:  
**QualTek Molecular Laboratories**  
**MISP Receiving**  
**[name]**  
**[name]**  
**[contact]**  
**Email: [[contact]](mailto:[contact])**

## 10.0 STATISTICAL CONSIDERATIONS

For PFS, assumptions are that the addition of pembrolizumab will increase PFS to 5  
months compared to historical control of 3 months. Assuming exponential survival, with  
27 evaluable patients, there is 80% power to detect this difference using a one-  
tailed z test at  $p < 0.05$ .

Recruitment of 30 participants to accrue 27 evaluable will last approximately 30 months  
(2.5 years) and participants will be followed for a maximum of 2 years from enrollment of  
the last patient. The primary outcomes chosen is PFS based on mechanism of action..

PFS will be analyzed using a Kaplan-Meier curve. A confidence interval for the median  
PFS will be calculated (Brookmeyer, R. and Crowley, J. (1982), "A Confidence Interval for  
the Median Survival Time," *Biometrics*, 38, 29-41.), and if the confidence interval is  
totally above 3 months, then it may be concluded that the PFS exceeds 3 months.

Objective response rate will be summarized using a proportion and an exact 95% binomial confidence interval. Anti-tumor activity will be reported as a percentage change in the sum of the dimensions of all measurable lesions as defined by RECIST 1.1 criteria. The baseline imaging before treatment will be compared to each subsequent imaging assessment. The maximum anti-tumor activity will be reported using the assessment with the smallest sum of dimensions (maximum response).

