
Statistical Methodology
	
For PFS, assumptions are that the addition of pembrolizumab will increase PFS to 5 months compared to historical control of 3 months. Assuming exponential survival, with 27 evaluable patients, there is 80% power to detect this difference using a one-tailed z test at p<0.05.
 
Recruitment will last approximately 30 months (2.5 years) and participants will be followed for a maximum of 2 years. The primary outcomes chosen is PFS based on mechanism of action. A total of 30 patients may be accrued in order to achieve 27 evaluable patients.

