#### 4.8 Patient Replacement

If a patient is withdrawn from the study prior to completing 21 days of therapy, for reasons other than adverse event or progression of disease, an additional patient may be added. If a patient discontinues treatment due to early progression prior to completing 3 cycles of therapy, the patient will be evaluable for toxicity but not for efficacy endpoints; in this case an additional patient may be added. (*Note: any patient receiving 1 dose of pembrolizumab is evaluable for toxicity but not for primary objective of PFS*).

Patients missing 14 or more doses of capecitabine due to toxicity will not be replaced.

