## 5.0 STUDY PROCEDURES

	Screening (-28 days)	On Treatment 		Off Treatment	
Time Period	Baseline	Cycle 1+ (+/- 3days)	After Every 3 cycles	End of Treatment	Follow-up 
Assessment or Activity					
Informed Consent	X				
Medical history (H)	X			X	
Concomitant Medications 	X	X		X	X 
Vitals, Physical exam  (PE) 	X	X		X	
ECOG status	X	X		X	
Toxicity assessment 		X		X	X 
Tumor Measurements 	X		X 	X	
Biopsy/archival tissue 	X				
CBC with diff 	X	X		X	
Chemistry panel 	X	X 		X	
PT/PTT/INR 	X				
Thyroid function tests 	X		X 		
Pregnancy test 	X				
Pembrolizumab 		X			
Capecitabine 		X			
Survival status					X

 Every physical exam will be a full physical exam and is standard of care. It will include vital signs (pulse, temperature, and blood pressure) and height (baseline only) and weight.

 CT c/a/p AND bone scan. In place of bone scan, a PET/CT may be used. If CT is contraindicated, MRI may be used. Any additional imaging such as MRI can be completed at the physician's discretion. The same modality should be used throughout the study. The baseline procedure is to be performed within 28 days prior to registration. Subsequently, it will be done prior to the start of the next treatment cycle e.g 4, 7, 10 etc. For patients who are unable to obtain scans at the designated time points, a window of 7-10 days is allowed. This exception is not applicable to the screening period. Bone scans are to be repeated at each time point ONLY if the patient has bone metastasis or if it is clinically indicated. If the original bone scan during screening is negative, then bone scans are not required in subsequent visits.

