## 6.0 ENDPOINT ASSESSMENT

### 6.1 Disease Definitions

Patients with non-measurable and measurable disease are eligible for this study. Response to treatment will be assessed using RECIST1.1 guidelines (Appendix 3). Response and progression will be assessed in this study via physical exam and imaging. Lesions are defined as either measurable or non-measurable using the criteria provided below.

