**PFS and ORR assessment (using irRECIST)**

To evaluate efficacy endpoint median-Progression Free survival (PFS), assessment will be done up to 1 year after discontinuation of the study drugs. Assessment will be done using irRECIST (see table below)

ORR will be assessed every 3 cycles (every 9 weeks) with imaging (CT chest/abdomen/pelvis and bone scan [if indicated]). Assessment will be done using irRECIST (see table below)

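### The 80% power belongs to a one-tailed exponential z test, but efficacy is decided by a median-PFS confidence interval of unstated level, which has about 40% power (95%) or 56% (90%) with 27 patients

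*Combined protocol and SAP*

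**What the plan says.** The Study Summary gives the design assumption, that pembrolizumab will "increase PFS to 5 months compared to historical control of 3 months", and the power: "Assuming exponential survival, with 27 evaluable patients, there is 80% power to detect this difference using a one-tailed z test", at a 0.05 level. Section 10.0 repeats both. The z test is mentioned nowhere else.

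Section 10.0 then sets out the analysis. PFS is summarised by Kaplan-Meier, a confidence interval for the median is computed by the cited Brookmeyer-Crowley method, and if that interval is "totally above 3 months, then it may be concluded that the PFS exceeds 3 months". The level, sidedness and transformation of the interval are not stated. The only level in the section is 95%, and it is for the response rate.

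Three other places bear on how the rule behaves:

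- **Scan timing.** Section 5.0, footnote 2, on scans after baseline: "Subsequently, it will be done prior to the start of the next treatment cycle e.g 4, 7, 10 etc". Section 6.3.3: "ORR will be assessed every 3 cycles (every 9 weeks) with imaging".
- **Progression by examination.** Section 6.1: "Response and progression will be assessed in this study via physical exam and imaging". Section 10.0 does not say how progression is dated.
- **Evaluability.** Under section 4.8, if a patient stops for progression before completing 3 cycles, "the patient will be evaluable for toxicity but not for efficacy endpoints". Sections 6.3.1 and 6.3.2 agree.

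**The concern.** The two procedures use the data differently. The exponential z test uses all follow-up time. The interval rule asks only whether the Kaplan-Meier estimate at 3 months is significantly above 0.5, and ignores how long patients remain progression-free after that. A power figure for the first says nothing about the second.

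This is the only decision rule for the primary endpoint of a single-arm trial. If its power is near 40%, a combination that truly achieves a 5-month median would more likely than not fail. If the level is chosen after the data are seen, a borderline result can be called either way.

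**Working it through.** **Inputs.** Medians of 3 and 5 months, exponential PFS, 27 evaluable patients, one-tailed 0.05 (Study Summary, section 10.0); scans every 9 weeks (sections 5.0 and 6.3.3). Assumptions: no censoring before 3 months, and one month = 30.4375 days.

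**1. The plan's own figure.** On the log scale the events needed are (1.645 + 0.842)² / ln(5/3)² = 23.7. With 27 events, power = Φ(ln(5/3)·√27 − 1.645) = 0.844. Simulation of this test gives 82% power and 3.5% size. The stated 80% is sound for that test.

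**2. The interval rule as a count.** Without censoring before 3 months, the linear lower limit exceeds 3 months when Ŝ − z·√(Ŝ(1 − Ŝ)/27) > 0.5, where Ŝ is the proportion progression-free at 3 months.

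- 95%: 19/27 gives 0.704 − 1.96 × 0.088 = 0.532, a pass. 18/27 gives 0.667 − 1.96 × 0.091 = 0.489, a fail.
- 90%: 18/27 gives 0.667 − 1.645 × 0.091 = 0.517, a pass. 17/27 gives 0.630 − 1.645 × 0.093 = 0.477, a fail.

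The true probability of being progression-free at 3 months is 0.5 at a 3-month median and 0.5^(3/5) = 0.660 at a 5-month median. Exact binomial results for n = 27:

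| Interval | Pass mark | Power (median 5) | One-sided size (median 3) |
|---|---|---|---|
| Linear 95% | ≥19 | 39.8% | 2.6% |
| Linear 90% | ≥18 | 55.9% | 6.1% |
| Log-log 95% | ≥20 | 25.1% | 1.0% |
| Log-log 90% | ≥19 | 39.8% | 2.6% |
| Log, 95% or 90% | ≥18 | 55.9% | 6.1% |

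A Kaplan-Meier simulation with 30 months' accrual and 24 months' follow-up gives 39.9% and 56.0% for the linear interval. Using all 30 patients changes little (40.0% and 55.3%). Power stays at or above 80% only from n = 75 (95%) or 59 (90%) with the linear form, and from 86 or 67 with log-log.

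**3. Progression dated only at scans.** The first scan is at 63/30.4375 = 2.07 months and the second is after 3 months, so the estimate at 3 months is really that at 2.07 months: 0.5^(2.07/3) = 0.620 or 0.5^(2.07/5) = 0.751. If half the progressions are dated as they occur and half at scans, the probabilities are (0.500 + 0.620)/2 = 0.560 and (0.660 + 0.751)/2 = 0.705.

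| Dating (linear rule) | Median 5: 95% / 90% | Median 3: 95% / 90% |
|---|---|---|
| As it occurs | 40% / 56% | 2.6% / 6.1% |
| Half and half | 60% / 75% | 9% / 18% |
| All at scans | 79% / 89% | 25% / 39% |

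The z test is not immune. If scan dates are treated as exact event times, it rejects 26% of the time at a 3-month median.

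**4. The powered test with interval-censored dating.** On the 9-week grid, each patient's number of progression-free scans is geometric with continuation probability 0.620 or 0.751. Rejecting when the total over 27 patients is at least 64 has exact size 0.045 and power 0.838.

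**5. Effect of the evaluability rule.** Suppose everyone progressing before day 63 is dropped and time still runs from the start of treatment. At a true 3-month median, the chance that a retained patient is progression-free at 3 months is 0.500/0.620 = 0.807. The linear rule then passes 94% (95% interval) or 98% (90%) of the time, and the z test rejects 69% of the time.

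**The case against.** The strongest reply is that 40% is not what the plan would deliver. Scans are 9 weeks apart, and dating progression at scans raises success at a 5-month median to 79% or 89%. Excluding early progressors raises it further. On that reading the likelier danger is false success, not low power. This is right as far as it goes, and it is why the low-power figures are tied to progression observed as it occurs. It does not rescue the plan: the gain comes with a false-positive rate of 25% or 39% against a stated 0.05. Progression found on examination falls somewhere between, and no section gives the split.

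A second reply is that 95% is the natural default, since section 10.0 uses it for response rate. But a one-tailed 0.05 test corresponds to a 90% two-sided interval. The two levels give different verdicts at 18 of 27.

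Third, the cited method paper may fix the interval's form, which cannot be checked from the documents. If so, some rows of the first table fall away. None of the forms shown there reaches 80%.

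Finally, the wording is permissive and this is a single-arm phase II trial. That softens the tone, but the documents contain no other efficacy rule.

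**Conclusion.** The concern holds and must be fixed. The 80% is a correct figure for a test the plan does not use to decide. For the rule it does use, power at 27 patients is 25% to 56% over the interval forms tabulated above, assuming exponential PFS, no censoring before 3 months, no exclusions and progression observed as it occurs. Under scan-only dating the failure moves to the false-positive rate. Neither dating gives 80% power at one-sided 0.05. The exact operating characteristics cannot be stated, because the interval's level and form and the dating of progression are all unspecified.

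**What to change.** In section 10.0 and the Study Summary, choose one:

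- **(a) Make the powered test the decision rule.** Use a one-sided 0.05 test of the hazard against ln 2/3 per month. Enter scan-detected progression as interval-censored between scans, and death or examination-detected progression at its date. Report the Kaplan-Meier median with a two-sided 90% interval as descriptive. The size of 0.045 and power of 0.838 apply to the pure 9-week grid with all 27 patients included and scans on time. They should be recomputed for the mixture of dating and for the 7-10 day scan window in section 5.0. This option leans on the exponential assumption already made.
- **(b) Keep the interval rule.** State its level and transformation and restate power as 40% / 56% (linear, 95% / 90%) or 25% / 40% (log-log), or the matching figure for another form. This matches the median-PFS objective and needs no hazard assumption for the test itself, but it admits low power. Restoring 80% would take 59 to 86 patients under the linear and log-log forms.

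Either way, state how progression is dated, and that the quoted figures assume it is observed as it occurs unless interval-censored. Say also that changing the test alone does not restore the error rates while sections 4.8, 6.3.1 and 6.3.2 leave early progressors out of the efficacy analysis; that rule needs its own change.

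The cost is a few sentences and no extra patients.
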